APPENDIX G. PROTOCOL AMENDMENT SUMMARY OF CHANGES

Document	Date
Amendment 1 (Version 2):	08 MAR 2021

Amendment 1 (08 MAR 2021)

Overall Rationale for the Amendment:

The primary purpose of this amendment is to incorporate additional dose levels to evaluate the safety and preliminary activity of INCB086550 with intermittent and/or step-down dose administration schedules. The changes are summarized below.

1. **Section 1, Protocol Summary (Table 2: Key Study Design Elements; Figure 1: Study Design Schema; Table 3: Schedule of Activities for 28-Day Cycle [Schedule A]; Table 4: Schedule of Activities for 28-Day Cycle [Schedule B]; Table 5: Schedule of Activities for 21-Day Cycle [Schedule C]; Table 6: Schedule of Activities for 21-Day Cycle [Schedule D]); Section 2.2.1, Scientific Rationale for Study Design; Section 2.2.2, Justification for Dose; Section 4.1, Overall Design; Section 6.1, Study Treatment Administered (Table 9: Study Treatment Administered)**

Description of change: Removed initial treatment regimen of 400 mg BID as the pharmacologically active dose that will be used initially and provided updated safety language from the Phase 1 study. Updated INCB086550 treatment administration to incorporate evaluation of intermittent and/or step-down dose administration regimens. Added a 21-day schedule of assessments as an option and added new SoA to accommodate the additional schedules (Tables 4-6).

Rationale for change: To enable the evaluation of safety and tolerability and preliminary efficacy of intermittent and/or step-down dose administration in 21-day or 28-day treatment cycles.

2. **Section 1, Protocol Summary (Table 2: Key Study Design Elements)**

Description of change: The number of participants planned to receive INCB086550 has been clarified as up to approximately 304 participants, rather than 152 participants, given that more than 1 level may be tested.

Rationale for change: Ability to add dose levels.

3. **Section 1, Protocol Summary (Figure 1: Study Design Schema); Section 4.1, Overall Design; Section 10.5, Interim Analysis**

Description of change: Added nonbinding safety and efficacy run-in analysis in up to 15 participants in select disease-specific cohorts.

Rationale for change: To enable the early evaluation of safety and efficacy.

4. Section 1, Protocol Summary (Table 3: Schedule of Activities for 28-Day Cycle [Schedule A]; Table 4: Schedule of Activities for 28-Day Cycle [Schedule B]; Table 5: Schedule of Activities for 21-Day Cycle [Schedule C]; Table 6: Schedule of Activities for 21-Day Cycle [Schedule D]); Section 8.5.1, Serum and Plasma for Correlative Assessments

Description of change: Added note to hematology panel that additional unscheduled CBCs may be performed. Added note to endocrine panel, plasma and serum for correlative studies, [REDACTED] that additional assessments may be performed if a participant has an irAE. Added a new collection of serum for correlative studies.

Rationale for change: To further evaluate immune activation and irAEs.

5. Section 1, Protocol Summary (Table 3: Schedule of Activities for 28-Day Cycle [Schedule A]; Table 4: Schedule of Activities for 28-Day Cycle [Schedule B]; Table 5: Schedule of Activities for 21-Day Cycle [Schedule C]; Table 6: Schedule of Activities for 21-Day Cycle [Schedule D]); Section 5.1, Inclusion Criteria (Inclusion Criterion 6); Section 8.3.6, Laboratory Assessments (Table 17: Required Laboratory Analytes); Section 8.3.6.1, Pregnancy Testing; Appendix A, Information Regarding Effectiveness of Contraceptive Methods

Description of change: Modified requirements for pregnancy testing and contraception based on Clinical Trials Facilitation and Coordination Group 2014 and 2020 guidance.

Rationale for change: Updated guidance.

6. Section 3, Objectives and Endpoints (Table 7: Objectives and Endpoints); Section 8.2, Efficacy Assessments; Section 8.2.1.2, Assessment of Disease Response During Treatment; Section 10.4, Statistical Analyses

Description of change: Removed evaluation of efficacy per iRECIST and option for treatment beyond progression.

Rationale for change: Not required.

7. Section 5.1, Inclusion Criteria

Description of change: Modified Inclusion Criterion 5.e to include chemotherapy as an allowable line of prior therapy and added Inclusion Criterion 7 to clarify that participants (except those with NSCLC) must have documented disease progression after treatment with available therapies.

Rationale for change: Clarification.

8. Section 6.1, Study Treatment Administered (Table 7: Study Treatment Information); Appendix C, Instruction to Participants for Handling Study Drug (INCB086550)

Description of change: Added INCB086550 400 mg tablet strength. Specified that INCB086550 tablets may be crushed and administered with water, apple juice, applesauce, or yogurt. Clarified language pertaining to doses for QD and BID dose schedules.

Rationale for change: Addition of new tablet strength and treatment administration method and clarification of QD and BID dose schedules.

9. Section 6.6.2, Restricted Medications and Procedures

Description of change: Added examples of P-gp inhibitors with a narrow therapeutic window as well as information pertaining to INCB086550 as an inhibitor of the creatinine transporter OCT2 and use of stomach acid-reducing medications such as proton pump inhibitors and H₂-receptor blockers.

Rationale for change: To provide examples of P-gp inhibitors and clarification on use of metformin (an OCT2 substrate) and stomach acid-reducing medications. [REDACTED]

10. Section 6.6.4, COVID-19; Appendix F, COVID-19 Pandemic Mitigation Strategies and Instructions

Description of change: Added information related to management of the study and participants during the COVID-19 pandemic.

Rationale for change: New information.

11. Section 1, Protocol Summary (Table 3: Schedule of Activities for 28-Day Cycle [Schedule A]; Table 4: Schedule of Activities for 28-Day Cycle [Schedule B]; Table 5: Schedule of Activities for 21-Day Cycle [Schedule C]; Table 6: Schedule of Activities for 21-Day Cycle [Schedule D]); Section 8.1.4, Distribution of Dosing Diary and Patient Information Cards

Description of change: Dosing diaries will also be provided for each patient at each visit.

Rationale for change: Clarification.

12. Section 8.2.1, Tumor Imaging by RECIST v1.1; Section 10.2, Populations for Analysis (Table 21: Populations for Analysis)

Description of change: Updated information for assessment of skin lesions according to RECIST v1.1 and the evaluable populations.

Rationale for change: Clarification.

13. Section 8.3.5, Electrocardiograms

Description of change: Revised Table 15 and added Table 16 to clarify the ECG collection schedule based on treatment schedule.

Rationale for change: Clarification.

14. Section 8.3.6, Laboratory Assessments (Table 17: Required Laboratory Analytes)

Description of change: Specified that free T4 and total T3 should be performed to evaluate endocrine function. Added requirement for IgM for HAV serology testing. Updated requirements for pregnancy testing.

Rationale for change: Clarification.

1. INTRODUCTION

This open-label, global, nonrandomized, multicohort trial is designed to provide a benchmark of efficacy for INCB086550 in key indications in which other PD-(L)1 inhibitors have already demonstrated efficacy.

Section 2 of the Protocol provides a detailed description of the investigational product, rationale for doses to be examined, and potential risks and benefits of treatment with INCB086550.

The purpose of this SAP is to provide details of the statistical analyses that have been outlined in INCB 86550-203 Protocol Amendment 1. The scope of this plan includes the analyses that are planned and will be executed by the Department of Biostatistics or designee. Pharmacokinetic analysis will not be performed for this study. This study was terminated early.

2. STUDY INFORMATION, OBJECTIVES, AND ENDPOINTS

2.1. Protocol and Case Report Form Version

This SAP is based on INCB 86550-203 Protocol Amendment 1 dated 08 MAR 2021 and CRFs approved 30 MAR 2022. Unless superseded by an amendment, this SAP will be effective for all subsequent Protocol amendments and eCRF versions.

2.2. Study Objectives and Endpoints

Table 1 presents the objectives and endpoints.

Table 1: Objectives and Endpoints

3. STUDY DESIGN

This study is a Phase 2, open-label, global, multicenter study designed to assess the clinical activity and safety of INCB086550 as initial immune checkpoint inhibitor therapy in participants with advanced selected solid tumors in which the efficacy of PD-(L)1 inhibitors has previously been established. Participants will be enrolled at 1 or more dose levels into disease-specific cohorts (see Figure 1), with a safety/efficacy run-in analysis in up to 15 participants and a nonbinding interim futility analysis planned after approximately 50% of the participants in each cohort are evaluable for response using the RECIST evaluable population. This study was terminated early.

[figure not shown]
The primary endpoint is confirmed ORR as determined by the investigator using RECIST v1.1.

The study consists of 3 periods: screening, study drug treatment, and follow-up.

A maximum study treatment duration of 2 years is allowed. Participants who achieve a CR may discontinue INCB086550 after 4 additional cycles (with a minimum of 1 year of treatment) upon consultation with the medical monitor.

The follow-up period will begin once a participant has completed 2 years of study treatment or has met criteria for discontinuation from study drug. Participants will be evaluated for AEs (including irAEs) for 90 days after the last dose of study drug.

Figure 1: Study Design Schema

^a Information on dosing is included in Protocol Section 2.2.2.

3.1. Randomization

Not applicable.

^b Nonbinding efficacy run-in is planned after enrollment of up to 15 participants in select disease-specific cohorts are evaluable for response using the RECIST evaluable population.

^c Nonbinding interim futility analyses are planned after approximately 50% of the participants in each diseasespecific cohort are evaluable for response using the RECIST evaluable population.

^dPD-L1 staining assessed using the Dako PD-L1 IHC 22C3 pharmDx assay.

3.2. Control of Type I Error

Not applicable.

3.3. Sample Size Considerations

The number of participants based on a group sequential design with 1 interim per cohort at approximately 50% information using a Hwang-Shih-DeCani (1990) spending function has been determined independently for each disease-specific cohort (irrespective of dose level) and can be found in Table 2. The target ORR (p₁) for each cohort is based on published clinical experience with a reference PD-1 inhibitor (El-Khoueiry et al 2017, Keytruda 2018, Mok et al 2019, Motzer et al 2015, Reck et al 2016, Robert et al 2015). The target ORR (p₁) for the NSCLC cohort was calculated by combining 2 different studies (Mok et al 2019, Reck et al 2016). The null ORR (p₀) for the melanoma and RCC cohorts is based on the control arm ORRs in the reference studies. For the NSCLC, UC, and HCC cohorts, the null ORR (p₀) was selected to be the p₀ that creates a test with a rejection region that begins with the lower CI bound of the reference PD-1 inhibitors. The sample size for each cohort provides approximately 80% power and 5% 1-sided Type I error.

Table 2: Sample Size per Cohort

	ORR		
Tumor Type (Cohort)	$\mathbf{p_0}$	p_1	Sample Size
NSCLC	18.0%	41.1%	32
UC	20.0%	47.0%	25
НСС	6.0%	20.0%	42
RCC	5.0%	25.0%	23
Melanoma	11.9%	32.9%	30

3.4. Schedule of Assessments

Refer to Protocol Amendment 1 dated 08 MAR 2021 for a full description of all study procedures and assessment schedules for this study.

4. DATA HANDLING DEFINITIONS AND CONVENTIONS

4.1. Scheduled Study Evaluations and Study Periods

4.1.1. Day 1

Day 1 is the date that the first dose of study drug (INCB086550) is administered to the participants.

4.1.2. Study Day

If a visit/reporting date is on or after Day 1, then the study day at the visit/reporting date will be calculated as

```
\text{Day } \# = (\text{visit/reporting date} - \text{Day 1 date} + 1).
```

If the visit/reporting date is before Day 1, then the study day at the visit/reporting date will be calculated as

```
Day \# = (visit/reporting date - Day 1 date).
```

A study day of -1 indicates 1 day before Day 1.

4.1.3. Baseline Value

Baseline is the last nonmissing measurement obtained before the first administration of INCB086550.

When scheduled assessments and unscheduled assessments occur on the same day and the time of the assessment or time of first dose is not available, use the following convention to determine baseline:

- If both a scheduled and an unscheduled visit are available on the day of the first dose and the time is missing, use the scheduled assessment as baseline.
- If all scheduled assessments are missing on the day of the first dose and an unscheduled assessment is available, use the unscheduled assessment as baseline.

4.1.4. Handling of Missing and Incomplete Dates

In general, values for missing dates will not be handled unless methods for handling missing dates are specified in this section or relevant sections. The original reported dates collected on the eCRF should be used in all relevant listings. The following rules will be used for handling partial dates for analyses requiring dates.

When calculating the time since diagnosis of cancer, a partial cancer diagnosis date will be handled as follows in the calculation:

- If only the day is missing, then the first day of the month will be used.
- If both the month and day are missing, then 01 JAN of the year will be used.
- If the diagnosis date is completely missing, then the time since diagnosis will not be calculated.

When the date of the last dose is used in deriving variables such as duration of treatment or TEAE flag, a missing or partial date of the last dose will be handled as follows:

- If only the day is missing, then the earlier date of the last day of the month or the date that the participant discontinued treatment will be used.
- If both the month and day are missing, then the earlier date of 31 DEC of the year or the date that the participant discontinued treatment will be used.
- Otherwise, the date that the participant discontinued treatment will be used as the date of the last dose.

For DOR, partial date of the death date will be handled as follows in the calculation:

- If mmyyyy for the last known alive date = mmyyyy for the death date, then the death date will be set to the day after the last known alive date.
- If mmyyyy for the last known alive date < mmyyyy for the death date, then the death date will be set to the first day of the death month.
- Otherwise, the partial death date will not be imputed.

4.1.5. Cycle Length and Duration

Cycle 1 Day 1 is the day that the first dose of study drug is administered. The scheduled cycle length is either 21 or 28 days (Protocol Tables 3-6). The actual Day 1 of subsequent cycles will correspond with the first day of administration of INCB086550 in that cycle; thus, treatment cycles may become out of sync with the originally planned schedule, and the cycle length may be different from 21 or 28 days. The date of the Day 1 of subsequent cycles recorded on the eCRF will be used as the Day 1 of the subsequent cycles.

4.2. Variable Definitions

4.2.1. Prior and Concomitant Medication

Prior medication is defined as any nonstudy medication started before the first dose of INCB086550.

Concomitant medication is defined as any nonstudy medication that is started accordingly:

- Before the date of first administration of INCB086550 and is ongoing throughout the study or ends on/after the date of first study drug administration.
- On/after the date of first administration of INCB086550 and is ongoing or ends during the course of the study.

A prior medication could also be classified as "both prior and concomitant medication" if the end date is on or after the first dose of INCB086550. In the listing, it will be indicated whether a medication is only prior, only concomitant, or both prior and concomitant.

For the purposes of analysis, all medications will be considered concomitant medications unless the medications can unequivocally be defined as not concomitant.

5. STATISTICAL METHODOLOGY

5.1. General Methodology

Unless otherwise noted, SAS® software (SAS Institute Inc, Cary, NC; v9.4 or later) will be used for the generation of all tables, graphs, and statistical analyses. Descriptive summaries for continuous variables will include but not be limited to the number of observations, mean, standard deviation, median, minimum, and maximum. Descriptive summaries for categorical variables will include the number and percentage of participants in each category.

Interim analyses are planned for this study as defined in Section 10; however, the study was terminated early, and no interim analyses will be performed.

5.2. Treatment Groups

Participants will be enrolled at 1 or more dose levels into disease-specific cohorts, with a safety/efficacy run-in analysis in up to 15 participants. The study was terminated prior to completion of the safety/efficacy run-in analysis. Data will be summarized separately for each cohort and dose level and may be summarized in total, as appropriate depending on enrollment.

5.3. Analysis Populations

Table 3 presents the populations for analysis. Table 4 presents the analysis populations by endpoint.

Table 3: Populations for Analysis

Population	Description
FAS	The FAS includes all study participants who received at least 1 dose of study drug. The FAS will be used for the summary of demographics, baseline characteristics, participant disposition, and all efficacy analyses. Participants will be analyzed according to the treatment group/dose to which they have been assigned.
Safety evaluable	The safety evaluable population includes all participants who received at least 1 dose of study drug. All safety analyses will be conducted using the safety evaluable population. Treatment groups for this population will be determined according to the actual treatment group/dose the participant received regardless of assigned study drug treatment.

 Table 4:
 Analysis Populations by Endpoint

Endpoint	Analysis Population
ORR, defined as the percentage of participants with a best overall response of CR or PR confirmed by at least 1 repeat assessment ≥ 28 days later according to RECIST v1.1 as determined by the investigator.	FAS
DCR, defined as the percentage of participants with a best overall response of CR or PR confirmed by at least 1 repeat assessment \geq 28 days later, or SD for \geq 12 weeks, by investigator assessment per RECIST v1.1.	FAS
DOR, defined as the time from the earliest date of CR or PR confirmed by at least 1 repeat assessment ≥ 28 days later until the earliest date of disease progression by investigator assessment per RECIST v1.1, or death due to any cause, if occurring sooner than progression.	FAS
Safety is determined by monitoring the frequency and severity of AEs, including the evaluation of laboratory tests, vital signs, and ECGs.	Safety evaluable

6. BASELINE, EXPOSURE, AND DISPOSITION

Appendix A provides a list of data displays. Sample data displays are included in a separate document.

6.1. Demographics, Baseline Characteristics, and Disease History

6.1.1. Demographics and Baseline Characteristics

The following demographics and baseline characteristics will be summarized for the FAS: age, sex, race, ethnicity, weight, and height.

6.1.2. Baseline Disease Characteristics and Disease History

The following baseline disease characteristics and disease history will be summarized for the FAS: ECOG PS, cancer type, current stage, current sites of metastatic disease, and PD-L1 TPS for participants with NSCLC and participants with UC. Relevant

6.1.3. Prior Anticancer Therapy

Prior anticancer therapy will be listed.

6.1.4. Medical History

Medical history will be listed.

6.2. Disposition of Participants

The number and percentage of participants who were treated, who were ongoing with study treatment, who completed study treatment, who discontinued study treatment with a primary reason for discontinuation, who were still in the study, who completed the study, and who withdrew from the study with a primary reason for withdrawal will be summarized for the FAS. The number of participants enrolled by country and/or site will also be provided by cohort and dose level.

6.3. Protocol Deviations

Important Protocol deviations will be summarized and listed for the FAS.

6.4. Exposure

For participants in the safety evaluable population, exposure will be summarized as follows:

- **Duration of treatment with INCB086550 days:** (date of last dose of INCB086550 date of first dose of INCB086550 + 1) (including scheduled dose holds [days] for intermittent schedule).
- Average daily dose of INCB086550 (mg/day): total actual INCB086550 dose taken (mg) / duration of treatment with INCB086550 (days).

Total actual dose taken will be calculated based on the information entered on the Dosing eCRF.

6.5. Study Drug Compliance

For participants in the safety evaluable population, overall compliance (%) for INCB086550 will be calculated for all participants as follows:

compliance (%) = $100 \times [\text{total dose actually taken}] / [\text{total prescribed dose}].$

The total prescribed dose is defined as the sum of the doses prescribed by the investigator accounting for dose modifications.

The total actual dose taken will be calculated based on information entered on the Dosing eCRF.

6.6. Prior and Concomitant Medications

Prior medications and concomitant medications will be listed.

7. EFFICACY

Appendix A provides a list of data displays. Sample data displays are included in a separate document.

7.1. Efficacy Hypotheses

Not applicable.

7.2. Analysis of the Primary Efficacy Parameters

7.2.1. Response Criteria

Overall disease status will be categorized using RECIST v1.1 (Eisenhauer et al 2009). Participants will have their overall response evaluated as CR, PR, SD, PD, or NE at each postbaseline radiologic assessment based on changes in target lesions, nontarget lesions, and appearance of new lesions.

7.2.2. Best Overall Response

In general, under RECIST v1.1, best overall response is the best response recorded postbaseline prior to and including the first PD, in the order of CR, PR, SD, PD, and NE. The best overall response will be determined from response assessments prior to or on the same day as new anticancer therapy. If any alternative cancer therapy is taken while on study, any subsequent assessments will be excluded from the best overall response determination.

In the case of SD, measurements must meet the SD criteria at least once after the date of first dose at a minimum interval of 12 weeks. Participants who fail to meet this criterion will have best overall response of PD if the next available assessment indicates PD or NE if there is no additional assessment available.

The participant's best overall response assessment will depend on the achievement of both measurement and confirmation criteria in Table 5, with confirmation assessment occurring after a gap of ≥ 28 days.

Table 5: Confirmed Response Based on Subsequent Assessments

First Timepoint Response	Second Timepoint Response	Confirmed Response
CR	CR	CR or SD or NE ^a
CR	PR ^b	SD or NE ^c
CR	PR ^b	SD or NE ^c
CR	PD	SD or NE ^c
CR	NE	SD or NE ^c
CR	No further evaluation	SD or NE ^c
PR	CR	PR or SD or NE ^d
PR	PR	PR or SD or NE ^e
PR	SD	SD or NE ^c
PR	NE	SD or NE ^c
PR	PD	SD or NE ^c
PR	No further evaluation	SD or NE ^c
SD	CR	SD or NE ^c
SD	PR	SD or NE ^c
SD	SD	SD or NE ^c
SD	PD	SD or NE ^c
SD	NE	SD or NE ^c
SD	No further evaluation	SD or NE ^c
PD	No further evaluation	PD
NE	CR	NE
NE	PR	NE
NE	SD	NE
NE	PD	NE
NE	NE	NE
NE	No further evaluation	NE

Note: A confirmed response of SD can only be made after the participant is on study for a minimum of 12 weeks according to the study Protocol or SAP. If the participant is on study less than 12 weeks, any tumor assessment indicating SD before this time period will have a confirmed response of NE. NE is not required to be confirmed according to the table.

Note: Subsequent documentation of CR may provide confirmation of a previously identified CR for participants where the second integrated response was NE. Subsequent documentation of PR may provide confirmation of a previously identified PR for participants where the second integrated response was NE or SD. If the third tumor assessment confirms the CR (or PR), then the confirmed response will be CR (or PR). Only 1 intervening NE is allowed between CRs/PRs. For example: CR NE CR = CR; PR NE PR/CR = PR. Additionally, 1 SD (≥ 25% reduction in target lesions comparing with baseline) is allowed between PRs (eg, PR SD PR/CR = PR). Note: in the scenario of PR SD NE PR, this is not a confirmed PR.

- ^a Confirmed response is CR if 28-day gap is met. Otherwise, confirmed response is SD if at least 12 weeks on study or NE if within 12 weeks on study.
- ^b Special case programming: assign PR or SD following CR as PD in confirmed response.
- ^c Confirmed response will be SD if the first tumor assessment is at least 12 weeks on study. Otherwise, the confirmed response will be NE.
- d Confirmed response is PR if 28-day gap is met. Otherwise, confirmed response is SD if at least 12 weeks on study or NE if within 12 weeks on study.

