8.2.1.2. Assessment of Disease Response During Treatment

The first imaging assessment should be performed 8 weeks (56 ± 7 days) after the first dose of INCB086550 and then every 8 weeks (56 ± 7 days) for the first 6 months. After 6 months of study treatment, imaging frequency may be reduced to every 12 weeks (84 ± 14 days).

Participants who discontinue study treatment for a reason other than disease progression should continue to have efficacy assessments performed according to the original schedule following their final on-study treatment scan until disease progression as determined by RECIST, new anticancer therapy is started, death, withdrawal of consent, or end of study. Imaging assessments may be performed more frequently if clinically indicated.

Complete response or PR should be confirmed by imaging at least 4 weeks after the initial documentation.

Imaging should follow calendar days and should not be delayed for delays in cycle starts.

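### SAP 7.2.2 gives two results for SD at the first scan followed by PD: PD in the text, NE in Table 5

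*SAP*

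**What the plan says.** SAP 7.2.2 (Best Overall Response) gives three instructions that bear on this point.

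- **General order.** Best overall response is the best post-baseline response up to and including the first PD, ranked CR, PR, SD, PD, NE.
- **Rule for short SD.** For SD, "measurements must meet the SD criteria at least once after the date of first dose at a minimum interval of 12 weeks". If that is not met, "Participants who fail to meet this criterion will have best overall response of PD if the next available assessment indicates PD". The text keeps the other outcome for a participant with no later scan: "or NE if there is no additional assessment available".
- **Table 5.** The section says the "best overall response assessment will depend on the achievement of both measurement and confirmation criteria in Table 5". The rows SD then PD, PR then PD and CR then PD all lead to SD or NE under footnote c: "Confirmed response will be SD if the first tumor assessment is at least 12 weeks on study. Otherwise, the confirmed response will be NE". The row NE then PD leads to NE. A note under the table adds that, for a participant on study for less than 12 weeks, "any tumor assessment indicating SD before this time period will have a confirmed response of NE".

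Protocol 8.2.1.2 sets the scan timing: "The first imaging assessment should be performed 8 weeks (56 ± 7 days) after the first dose of INCB086550", then every 8 weeks for the first 6 months. SAP Appendix A plans one efficacy table, Table 2.3.1, a summary of best overall response in the FAS.

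**The concern.** For early SD followed by PD, the text and the table in one section give different categories, and the section makes best overall response depend on that table. The path is an ordinary one: no progression at the week-8 scan, then progression at the next.

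PD and NE mean different things to a reader. PD says the disease progressed on treatment; NE says no judgement could be made. Two programmers working correctly from this section could fill those two rows of Table 2.3.1 differently. With few participants, as SAP 11.2.1 indicates, one reclassified participant is visible in the percentages.

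**Working it through.** The plan states no figure that depends on this rule, so there is none to reproduce. The check compares dates and then runs the rules on example scan sequences.

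**Dates.**
- First scan (Protocol 8.2.1.2): 56 − 7 = Day 49 to 56 + 7 = Day 63.
- SD minimum (SAP 7.2.2): 12 × 7 = 84 days.
- 84 − 63 = 21 days. Every in-window first scan is therefore at least 21 days short, and footnote c always selects NE for it.

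**Rules applied.** The second column uses the text rule for short SD. The third uses the Table 5 row for the first two scans, with footnote c cut at Day 84. The fourth applies Table 5 to each scan in turn up to the first PD and then takes the best result in the order CR, PR, SD, PD, NE.

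| Scans | Text rule | Table 5, first pair | Table 5 scan by scan, then order |
|---|---|---|---|
| SD Day 49, PD Day 105 | PD | NE | NE, PD: PD |
| SD Day 56, PD Day 112 | PD | NE | NE, PD: PD |
| SD Day 63, PD Day 119 | PD | NE | NE, PD: PD |
| PR Day 56, PD Day 84 or 112 | no specific rule | NE | NE, PD: PD |
| CR Day 56, PD Day 112 | no specific rule | NE | NE, PD: PD |
| NE Day 56, PD Day 112 | no specific rule | NE | NE, PD: PD |
| SD Day 56, no later scan | NE | NE | NE |
| SD Day 56, SD Day 112, PD Day 168 | SD | NE | NE, SD, PD: SD |
| SD Day 56, PR Day 112, PR Day 168 | no specific rule | NE | NE, PR, SD: PR |

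The first three rows are the direct contradiction. The next three conflict only with the general order. The last two show that Table 5 cannot be meant for the first pair alone: SD confirmed at week 16 would be lost, and a response first seen at week 16 could never be confirmed.

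**Effect on the endpoints.** SAP Table 4 assigns ORR and DCR to the FAS. On the affected paths PD and NE both add 0 to the numerator and 1 to the denominator, so neither rate moves. DOR covers confirmed responders only, and these participants are not among them.

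**Effect on Table 2.3.1.** Each reclassified participant shifts 100/n percentage points between PD and NE. The group size n is assumed, because the documents give no enrolment counts:
- n = 5: 20.0
- n = 10: 10.0
- n = 15: 6.7
- n = 30: 3.3

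**The case against.** The strongest reply is that Table 5 must be read scan by scan, as the last two rows of the check show. Once it is, the ranking of PD above NE is already written in the first sentence of 7.2.2, and Table 5 has a row in which PD is the first timepoint and the result is PD. The text also has an explicit rule for early SD then PD. On this view three routes lead to PD, and only one row read in isolation leads to NE.

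Most of that stands, and PD is very probably what was intended. But the SAP never says that Table 5 is applied to successive scans or how the row results are combined. Its notes cover only certain three-scan confirmations of CR and PR. The one row starting with PD is for no further evaluation, whereas Protocol 6.5.4 asks for a repeat scan after PD. The SD-then-PD row does not list PD as an outcome at all. The conflict therefore remains as written.

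Stronger readings are tempting, and the documents do not support them:
- A reader might infer that PR then PD is the same direct contradiction. It is not: the specific text rule covers SD only. PR, CR and NE followed by PD conflict only with the general order.
- A reader might infer that every participant progressing at the second scan will be misclassified, or put a percentage on them. Under the scan-by-scan reading none is misclassified, and the documents give no frequency for this path.
- A reader might infer that progression would be hidden from the report. Listings 2.6.1 and 2.6.3 to 2.6.5 would still show the response assessments and lesion data for each participant.

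**Conclusion.** The point holds in a limited form. For SD at an in-window first scan followed by PD, SAP 7.2.2 states both PD and NE. For PR, CR or NE followed by PD, Table 5 gives an NE that is inconsistent with the section's own order. Because the step that would resolve this is not written, progressors can be reported as NE in Table 2.3.1; that they will be is not established.

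The consequence is confined to the PD and NE counts in that table. This rests on two things: the first scan is done within its window, and the FAS is the denominator. A first scan delayed to Day 84 or later, which the COVID-19 allowance in Protocol Appendix F could permit, would give SD under both the text and the table. How many participants are affected cannot be stated from the documents.

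**What to change.** Amend SAP Table 5 and add one sentence to 7.2.2:

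1. For SD then PD, PR then PD and CR then PD: the result is SD if the first assessment of the pair is at least 12 weeks on study, otherwise PD.
2. For NE then PD: the result is PD.
3. State that Table 5 is applied to each successive assessment up to the first PD, and that best overall response is the best of the results in the order CR, PR, SD, PD, NE.
4. Make the Table 5 note on SD before 12 weeks subject to item 1, so that it does not reintroduce NE when PD is found before week 12.

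A general rule confining NE to sequences with no later evaluable assessment should not be added. It would leave other early sequences, such as SD then SD or PR then SD with both scans before 12 weeks, without a defined result.

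The cost is a footnote change, one sentence and a matching check in the programming specification. No new data are needed, and ORR, DCR and DOR stay as they are.
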